## \*Pay participant \$40 Amazon gift card incentive if ineligible based on BP\*

If participant is ineligible due to high BP and is not currently on BP meds but states that they plan to start taking BP-lowering medications (per their PCP's recommendation/prescription) within the study recruitment period, they can be offered to reach out the study team via phone/email when their BP has stabilized. The same protocols will apply (confirming BP for eligibility) at the visit. If they are still ineligible due to high BP at that point, no other follow-up will occur and they will not be randomized.

IF AVERAGE BP IS IN-RANGE (SBP: 120-159 OR DBP: 80-99 OR BOTH)

- Once AVERAGE BP is verified as being in-range: (SBP 120-159 OR DBP 80-99 OR BOTH), Staff continue with randomization and orientation to the treatment arm, as described above
- At the end of the visit, pay the participant \$40 Amazon gift card incentive.

#### Follow-up Visits 3, 4, 5, 6 (Follow-up Months 2, 4, 6, 12)

- 2 weeks before each scheduled follow-up visit, ASA24 prompts are sent with reminders to be completed with reminders (as described above)
  - o If both ASA24s are not complete, can still do visit and prompt participant to complete the recall while in the visit:
    - Take BP
    - Ask ppt to log into ASA system with their information
    - Confirm medications and dosage
    - Administer surveys, if appropriate
    - Schedule next visit
  - O At end of visit, pay participant incentive (Amazon e-gift card):
    - \$20 for 2-month visit (Visit 3)
    - \$20 for 4-month visit (Visit 4)
    - \$40 for 6-month visit (Visit 5)
    - \$40 for 12-month visit (Visit 6)
- Automated reminders (REDCap emails)
  - O Appt needs to be confirmed with reminders for remote BP collection
- Send out online surveys for months 6 and 12 months to save time at appt:
  - o BP adherence med measures
  - o Physical activity
  - o Self-efficacy for healthy eating
  - Psychosocial measures (sleep, depression, stress, intuitive eating, etc)
  - O Personalization survey (months 2 and 4 only as intervention ends at month 6) for Ix arm only
- 6-month visit protocol will include reminders about not receiving any more feedback and satisfaction (see 6-month protocol)
- 9-month retention protocol (see 9-month protocol)
- 12-month visit protocol will include closing out participation in the study:
  - O Thank them for participating over the last year.
  - O Share free dietary tracking app resources (Nourish app is turned off)- e.g. Nutritionix, My Fitness Pal, that have nutritional data, etc.

## STATISTICAL ANALYSIS PLAN

We hypothesize that the intervention will lead to an increase in average DASH score of 2 units at 6 months and the control arm will achieve a 1-unit increase in DASH score. These estimates are based on the pilot study we conducted where both intervention and control arms achieved a 1-unit increase in DASH adherence from baseline to 3 months. Given the Nourish intervention is more intensive than what was delivered in the pilot, we anticipate a greater increase in DASH adherence. We estimate a standard deviation of 2 units for both intervention and control arms. This results in an effect size of 0.5, which is considered a medium effect size by Cohen's d. With 90% power and a type I error rate (alpha) of .01, a sample size of 242 will allow us to detect a difference of 1 unit in DASH adherence mean change score between study arms. We conservatively assume 20% attrition for this length of follow-up, resulting in the final analytic sample size of 300 total participants. With this sample size, we will also have power to examine intervention effects in systolic and diastolic blood pressure. Using data from the pilot study we anticipate systolic blood pressure changes in intervention vs control as follows: -3.4 (SD=8.6) mmHg and -2 (SD=9.3) mmHg respectively, which results in an effect size of 0.6. The effect size for diastolic blood pressure is 0.75 based on changes in intervention vs control of -3.8 (SD=7.9) mmHg vs. -1.6 (SD=6.4) mmHg, respectively. With 90% power and a type I error rate (alpha) of .01, we can detect the expected effect size with the proposed sample size of 300.

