# STUDY PROTOCOL

## Research Abstract

Over 100 million Americans suffer from high blood pressure and thus are at increased risk for cardiovascular disease and premature morality. Evidence supports the DASH (Dietary Approaches to Stop Hypertension) dietary pattern to reduce blood pressure. DASH is rich in fruits and vegetables, legumes, lean protein, and low-fat dairy, and reduced in red meats, sweets and processed foods. In the past 20 years, numerous trials have demonstrated the blood pressure-lowering effects of DASH across a diverse range of populations. As such, DASH is part of national dietary and blood pressure guidelines. Despite this strong evidence, fewer than 1% of U.S. adults with high blood pressure fully meet DASH guidelines. Like most efficacious interventions, the rate-limiting step involves dissemination. Behavioral trials testing DASH have been delivered primarily in-person, an approach that is effective but not accessible to the broader population. Innovative and accessible strategies to disseminate DASH, such as digital health, are critically needed. To address this need, we developed and tested the feasibility of a 3-month digital health intervention called DASH Cloud. The DASH Cloud intervention asked participants to track their diet daily using a commonly-used commercial tracking app with an extensive nutrient database. Our intervention technology platform extracted food and nutrient data from the app using an application programming interface (API). Each day, using this API software, we compared individual participant's nutrient intake to the recommended levels in the DASH diet. We then processed the data against an algorithm and sent automated text messages to each participant with information on DASH diet adherence and diet tips. Results indicated that we successfully recruited and retained individuals with elevated blood pressure, achieved high engagement with daily diet tracking and saw positive changes in diet quality. Based on the results of the feasibility trial, we will improve upon the personalization of the automated text messages and include a scalable and responsive way of delivering coaching, based on diet data received in the app. The efficacy of this approach will be tested via a fully-powered 12-month randomized controlled trial, Nourish. The trial will examine the effects of the intervention on changes in dietary quality and blood pressure among men and women with high blood pressure, using the new blood pressure guidelines for nonpharmacological treatment. The primary outcome is 6-month change in DASH adherence, as measured by 24-hour recalls. We will also measure DASH adherence at 12-months post-randomization. Secondary outcomes include changes in blood pressure and other physiological outcomes (e.g. weight, lipids, glucose). The scientific premise of this proposal represents establishing the efficacy of a previously deemed feasible approach for disseminating the DASH diet. With the millions of Americans in dire need of nonpharmacological treatments for blood pressure, the public health impact of disseminating the Nourish intervention could drastically reduce the incidence of cardiovascular disease. The findings from this study prepare us for a future implementation trial, testing the potential to implement DASH Cloud within clinics and other healthcare institutions, yielding

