#### **RCT**:

Power and sample size. Using data from the pilot study we anticipate systolic blood pressure changes in intervention vs control as follows: -3.4 (SD=8.6) mmHg and 2 (SD=9.3) mmHg which results in an effect size of 0.6. The effect size for diastolic blood pressure is 0.75 based on changes in intervention vs control of -3.8 (SD=7.9) mmHg vs. 1.6 (SD=6.4) mmHg. With 90% power and a type I error rate (alpha) of .01, we can detect the expected effect size with the proposed sample size of 300.

Demographic and baseline data will be examined for integrity of randomization scheme and the homogeneity of study arms. If any demographic and baseline data are not balanced between the two study arms and are believed to affect the outcome, we will consider adjusting these variables in the modeling process. All analyses will be based on intention-to-treat (ITT) principles.

Aim 1: To understand how DASH score improves over time from baseline to 6 months and sustains through 12-month follow-up between study arms, we will plot observed DASH score vs. time (baseline, 1- month, 2-month, 4-month, 6-month, 12-month) by two study arms. Linear mixed models will be built to test the primary hypotheses. If we observe a linear trend in the previous plot, our model will contain fixed effects including group variable (intervention vs. control), time, and intervention by time interaction. To account for the correlations within the same participant over time, we include a random intercept and random slope for time in the model. If there is a quadratic trend in time, we will also include a quadratic term in time in the model. If any of the demographic or baseline variables are statistically different between the two study arms, then these variables will be included in a step-wise model selection process for the linear mixed model. We will estimate model parameters using the SAS/STAT procedure MIXED (SAS Version 9, Cary, NC). We will evaluate the primary hypotheses by testing the null hypothesis that the time by intervention parameter is 0.

Aims 2 and 3: Similar analysis will be conducted for changes in blood pressure (Aim 2) and relevant clinical, behavioral and psychosocial variables (Aim 3). If the distribution of any of the outcomes is heavily skewed, then we will either appropriately transform the data so it's normally distributed or use a generalized linear mixed model with an appropriate link function.

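### The protocol and the SAP give opposite signs for the control-arm blood-pressure changes, and the SAP's figures do not yield its effect sizes of 0.6 and 0.75

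*Combined protocol and SAP*

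**What the plan says.** Two current paragraphs give the planning figures for blood pressure, and both name the pilot study as the source.

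- **Protocol** (Data Analysis & Statistical Considerations, RCT, power and sample size). Systolic: an intervention change of minus "3.4 (SD=8.6) mmHg and 2 (SD=9.3) mmHg which results in an effect size of 0.6". Diastolic: "changes in intervention vs control of -3.8 (SD=7.9) mmHg vs. 1.6 (SD=6.4) mmHg", with a stated effect size of 0.75. The control values carry no sign, so the plain reading is a rise of 2 and 1.6 mmHg.
- **SAP** (first paragraph under Statistical Analysis Plan). Systolic: an intervention change of minus "3.4 (SD=8.6) mmHg and -2 (SD=9.3) mmHg respectively, which results in an effect size of 0.6". Diastolic: "The effect size for diastolic blood pressure is 0.75 based on changes in intervention vs control of -3.8 (SD=7.9) mmHg vs. -1.6 (SD=6.4) mmHg". Here the control arm falls by 2 and 1.6 mmHg.

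The SAP says that with the DASH-driven sample size "we will also have power to examine intervention effects in systolic and diastolic blood pressure", and closes with 90% power at alpha .01: "we can detect the expected effect size with the proposed sample size of 300". The Research Abstract makes blood pressure secondary: "Secondary outcomes include changes in blood pressure and other physiological outcomes".

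**The concern.** The two paragraphs agree on the intervention changes, all four SDs, both effect sizes and the power claim. They disagree only on the sign of the control-arm change, for both outcomes, and neither explains why. The between-arm difference is 5.4 mmHg for both outcomes with the protocol's signs. With the SAP's signs it is 1.4 mmHg systolic and 2.2 mmHg diastolic. The same effect sizes cannot follow from both sets.

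At stake is the basis of the Aim 2 power statement, and what the documents say about the control arm: pressure rising or pressure falling. Anyone who reuses the SAP's figures, or reads a small or null blood-pressure result against them, needs to know which set is meant.

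**Working it through.** **Inputs.** Changes and SDs are those quoted above. Allocation is 1:1 (protocol, Design & Procedures). Alpha .01, 90% power, 300 participants and 20% attrition come from the SAP's power paragraph; 300 × 0.80 = 240 analysed.

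**Calibration on the plan's own figure.** The SAP's DASH calculation uses a difference of 1 and an SD of 2, so d = 0.5. A two-sample t-test (noncentral t) at two-sided .01 with 90% power needs 121 per arm, 242 in total, which is the SAP's number. One-sided .01 would need 212. The SAP does not state the sidedness; two-sided is inferred from this match.

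**Effect sizes.** d = |difference| / √((SD₁² + SD₂²)/2).

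- Systolic pooled SD: √((8.6² + 9.3²)/2) = 8.957
- Diastolic pooled SD: √((7.9² + 6.4²)/2) = 7.189

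| | Protocol signs | SAP signs | Stated |
|---|---|---|---|
| Systolic | (2 + 3.4)/8.957 = 5.4/8.957 = 0.603 | (3.4 − 2)/8.957 = 1.4/8.957 = 0.156 | 0.6 |
| Diastolic | (1.6 + 3.8)/7.189 = 5.4/7.189 = 0.751 | (3.8 − 1.6)/7.189 = 2.2/7.189 = 0.306 | 0.75 |

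**Could another SD explain the SAP's values?** With the SAP's signs and a single arm's SD:

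- Systolic: 1.4/8.6 = 0.163 and 1.4/9.3 = 0.151
- Diastolic: 2.2/7.9 = 0.278 and 2.2/6.4 = 0.344

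These also bound any pooling weighted by arm size. Reaching the stated values would need SDs of 1.4/0.6 = 2.3 and 2.2/0.75 = 2.9 mmHg, against stated SDs of 6.4 to 9.3.

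**Power** (two-sample t-test on change, two-sided .01, 120 or 150 per arm).

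| | d | Power, 240 analysed | Power, 300 analysed | Total analysed for 90% |
|---|---|---|---|---|
| Systolic, protocol signs | 0.603 | 98.0% | 99.6% | 168 |
| Diastolic, protocol signs | 0.751 | 99.9% | over 99.9% | 110 |
| Systolic, SAP signs | 0.156 | 8.5% | 10.9% | about 2,440 |
| Diastolic, SAP signs | 0.306 | 41% | 52% | about 640 |

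A looser test does not rescue the SAP's signs. At 300 analysed, one-sided .01 gives 16% and 62%, and two-sided .05 gives 27% and 75%.

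**Detectable difference.** The d detectable with 90% power is about 0.50 at 240 analysed and 0.45 at 300. In mmHg:

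- At 240: 0.50 × 8.957 = 4.5 systolic and 0.50 × 7.189 = 3.6 diastolic
- At 300: 0.45 × 8.957 = 4.0 systolic and 0.45 × 7.189 = 3.2 diastolic

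These depend on the SDs alone, so they hold whichever signs are right.

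**The case against.** The strongest reply is that this is two stray minus signs. Two separate effect sizes both match the protocol's signs to rounding. For the SAP's signs to be right, both effect sizes would have to be wrong and yet equal the positive-sign values by coincidence. That stands as an argument about the cause, and it is why the low-power branch should be read as a contingency and not as a finding that the trial is underpowered. It does not make the SAP paragraph correct.

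Second, part of the SAP's claim survives: effects of 0.6 and 0.75 are indeed detectable with 90% power at alpha .01, with 240 or 300 analysed. This also stands. What fails is the step from the printed changes to those effect sizes.

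Third, the systolic changes are introduced as anticipated values drawn from the pilot, and for DASH the SAP openly plans on a larger effect than the pilot showed. Pilot data alone might therefore not settle the question, so the check should extend to the power calculation itself.

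Finally, the text was read from PDF, and signs can be lost. But the signs differ for both outcomes and the SAP's wording differs slightly as well. Even if the protocol had lost two minus signs, the SAP would still contradict its own effect sizes.

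**Conclusion.** The point holds. The two paragraphs contradict each other on the control-arm changes, and the SAP's printed inputs give effect sizes of 0.16 and 0.31, not 0.6 and 0.75. The systolic effect size is overstated relative to those inputs by a factor of 5.4/1.4 = 3.9, and the diastolic by 5.4/2.2 = 2.5.

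A sign slip in the SAP is the likelier explanation, and the 90% claim then stands with room to spare. The pilot data are not in the documents, so this cannot be confirmed. If the negative values are right, the 90% claim fails for these planned differences.

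The consequence is confined to the power statement for a secondary outcome; the DASH calculation behind the 300 is untouched. The power figures assume a two-sided two-sample t-test on change scores. Power under the planned mixed model cannot be computed, because no within-person correlations are given. This should be fixed, but it is not a flaw in the design.

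**What to change.** Check the pilot data and the power calculation, then print one set of control-arm changes in both paragraphs.

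- **If the control changes are +2 and +1.6:** correct the two signs in the SAP. The effect sizes and the 90% claim stay.
- **If they are -2 and -1.6:** correct the protocol's signs. In both places, restate the effect sizes as 0.16 and 0.31 and the power as about 8–11% systolic and 41–52% diastolic. Give the differences detectable with 90% power at 240 analysed, about 4.5 and 3.6 mmHg. If the sponsor prefers to plan on a different target difference, state and justify it.

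In either case it would be better to quote blood-pressure power at about 240 analysed, in line with the 20% attrition assumption. This does not alter the conclusion.

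The cost is one data check and a corrected paragraph, with the matching protocol text if needed. Enrolment, endpoints, alpha and the analysis model do not change. The only loss, if the negative values prove right, is a less favourable power statement for Aim 2.

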## Statistical analysis plan

Demographic and baseline data will be examined for integrity of randomization scheme and the homogeneity of study arms. If any demographic and baseline data are not balanced between the two study arms and are believed to affect the outcome, we will consider adjusting these variables in the modeling process. All analyses will be based on intention-to-treat (ITT) principles.

We will assess the overall intervention effect on change of DASH score from baseline to 6 months by a two-sample t-test. To understand how DASH score improves over time from baseline to 6 months, and sustains through 12-month follow-up between study arms, we will plot observed DASH score vs. time (baseline, 2-month, 4- month, 6-month, 12-month) by two study arms. Linear mixed models will be built to test the primary hypotheses. If we observe a linear trend in the previous plot, our model will contain fixed effects including a group variable (intervention vs. control), time, and intervention by time interaction. To account for the correlations within the same participant over time, we will include a random intercept and random slope for time in the model. If there is a quadratic trend in time, we will also include a quadratic term for time in the model. To account for the stratified block randomization design, our models will also include our randomization stratification variables, blood pressure risk category and blood pressure medication status. If any other demographic or baseline variables are statistically different between the two study arms, then these variables will be included in a stepwise model selection process for the linear mixed model. We will evaluate the primary hypotheses by testing the null hypothesis that the time by intervention parameter is 0. Similar analysis will be conducted for changes in blood pressure and relevant clinical, behavioral and psychosocial variables. If the distribution of any of the outcomes is heavily skewed, then we will either appropriately transform the data so it's normally distributed or use a generalized linear mixed model with an appropriate link function.

Our linear mixed models will be fitted with a full maximum likelihood estimation using all available data to address missing data. These models allow for responses to be missing at random (MAR), where the missing mechanism may be related to either observed covariates or response variables, but not related to the unobserved data. Linear mixed models provide valid estimates of the intervention effect under the MAR mechanism and allow for a broad array of possible reasons for missingness.

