#### ASA-24 Protocol:

- Study team will assign ASA-24 login credentials for each participant based on the pre-coded list in REDCap
- Study team will log into ASA-24 website daily to confirm participant has completed ASA-24 measurements
- Study team will check ASA-24 website to confirm completion of survey and enter into ASA-2
  - O Dates between 2 ASA-24 submissions must be within 14-day window:
    - They have 3 attempts for each recall type (weekend or weekday)
- If participant completes 2 ASA-24 measurements within the 14-day period, the study team will receive automatic scheduling request email from RC to schedule a Zoom Visit 1 (Continue to STEP 3).
- If participant does not complete 2 ASA-24 measurements within the 14-day period, participant is ineligible.

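### A gain in precision at no cost: condition the 6-month DASH comparison on baseline, hold baseline means equal across arms in the mixed model, and delete the baseline-significance and stepwise covariate rules

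*Combined protocol and SAP*

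**What the plan says.** The Statistical analysis plan section gives two analyses of DASH score.

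- **6-month change.** "We will assess the overall intervention effect on change of DASH score from baseline to 6 months by a two-sample t-test". No covariates are named.
- **Mixed model over baseline, 2, 4, 6 and 12 months.** This is the model said to test the primary hypotheses. If the trend is linear, "our model will contain fixed effects including a group variable (intervention vs. control), time, and intervention by time interaction", with a random intercept and a random slope. Baseline is one of the outcome times, and the group term is free. Blood pressure risk category and medication status are always included.

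The same section has two further covariate rules. For variables that are unbalanced and thought to affect the outcome, "we will consider adjusting these variables in the modeling process". Then: "If any other demographic or baseline variables are statistically different between the two study arms, then these variables will be included in a stepwise" selection process. The protocol (Data Analysis & Statistical Considerations, RCT, Aim 1) has the same mixed model, without the t-test or the stratification terms, and the same trigger: "If any of the demographic or baseline variables are statistically different between the two study arms, then these variables will be included in a step-wise" selection.

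Two other statements bear on the point. The ASA-24 Protocol says: "If participant does not complete 2 ASA-24 measurements within the 14-day period, participant is ineligible". The sample-size paragraph of the SAP says that "a sample size of 242 will allow us to detect a difference of 1 unit in DASH adherence mean change score", and reports that in the pilot "both intervention and control arms achieved a 1-unit increase in DASH adherence from baseline to 3 months".

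**The concern.** Subtracting baseline is not the same as adjusting for it. A change score fixes the coefficient of baseline at 1. ANCOVA estimates that coefficient and, in large samples, is never less precise. The mixed model gives up precision in a related way: its free group term spends information on estimating a baseline difference that randomisation has already set to zero in expectation.

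Two completed recalls are an eligibility condition, so every randomised participant has a baseline DASH score and adjusting for it excludes nobody. The extra margin is useful here because the planned 1-unit difference has not been observed: the pilot arms rose by the same amount. If the true difference is smaller than planned, power falls quickly.

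The covariate rules are a separate matter. They use two different triggers, and neither has a significance level or a list of candidates. Significant baseline differences in a randomised trial arise by chance and do not show which variables predict the outcome. Two analysts could follow the SAP faithfully and fit different final models.

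**Working it through.** **Inputs from the documents.** Difference in mean change 1 unit; SD 2 units, used as the SD of change; alpha .01; power 90%; 1:1 allocation; 300 randomised; 20% attrition; model times 0, 2, 4, 6 and 12 months. Sidedness is not stated. Two-sided is assumed because it reproduces the stated size (one-sided gives 210).

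**Inputs assumed.** Correlation r between baseline and 6-month DASH score: 0.3 to 0.7, with equal SDs at the two times.

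**Step 1: reproduce the plan's figure.** d = 1/2 = 0.5. Under the noncentral t, 121 per arm gives power 0.9008, so N = 242, as stated. With 20% attrition from 300, 300 × 0.8 / 2 = 120 per arm, and power is 0.898.

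**Step 2: variance after conditioning on baseline.** With common SD s, the change-score variance is 2s²(1 − r) and the ANCOVA residual variance is s²(1 − r²). Their ratio is (1 + r)/2. The residual SD is therefore 2√((1 + r)/2).

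**Step 3: consequences at 120 per arm, two-sided alpha .01** (one further degree of freedom used for baseline).

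| | t-test on change | ANCOVA, r=0.3 | r=0.5 | r=0.7 |
|---|---|---|---|---|
| Variance ratio | 1 | 0.65 | 0.75 | 0.85 |
| Effective d for 1 unit | 0.500 | 0.620 | 0.577 | 0.542 |
| Power, 1 unit | 89.8% | 98.6% | 96.9% | 94.5% |
| Power, 0.75 units | 62.1% | 84.2% | 77.5% | 71.0% |
| Difference detectable with 90% power (units) | 1.00 | 0.81 | 0.87 | 0.92 |
| 99% CI half-width (units) | 0.67 | 0.54 | 0.58 | 0.62 |

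A simulation of 8,000 runs per setting agreed: ANCOVA power for 1 unit was 0.984, 0.968 and 0.944, and t-test power was 0.892 to 0.896.

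**Step 4: mixed model.** The table shows the generalised least squares variance of the group-by-time slope with baseline means constrained equal, divided by the variance with them free. The intraclass correlation is 0.3, 0.5 and 0.7, and the slope SD is in baseline SDs per month.

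| Times (months) | Slope SD | 0.3 | 0.5 | 0.7 |
|---|---|---|---|---|
| 0, 2, 4, 6 | 0 | 0.601 | 0.735 | 0.852 |
| 0, 2, 4, 6 | 0.05 | 0.628 | 0.759 | 0.873 |
| 0, 2, 4, 6, 12 | 0 | 0.698 | 0.815 | 0.903 |
| 0, 2, 4, 6, 12 | 0.05 | 0.768 | 0.870 | 0.943 |

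The last row is closest to the SAP, which includes a random slope and the 12-month visit.

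**Step 5: the covariate rules.** No screening level or number of variables is given. At an assumed 5% level with 10, 20 or 30 independent baseline variables, the probability that chance alone flags at least one is 1 − 0.95^k = 40%, 64% or 79%. Adding an imbalanced baseline variable as a main effect leaves the variance of the group-by-time term unchanged (ratio 1.000 with complete data). No loss of power or change in type I error is therefore attributed to these rules.

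**The case against.** The strongest reply is that the largest figures belong to the t-test, while the SAP says the mixed model tests the primary hypotheses. For that model the gain depends on how much individual slopes vary. At a slope SD of 0.10 the 0 to 12 month ratios become 0.86, 0.93 and 0.98; at 0.15 they become 0.92, 0.96 and 0.99. The ANCOVA range also assumes equal SDs: if the 6-month SD is 1.2 times the baseline SD, the ratios are 0.76, 0.87 and 0.97. At r = 0.8 with equal SDs, power for 1 unit is 93.0%. Both planned analyses are unbiased, and any test loses power when the true difference is smaller than planned. Finally, the first covariate rule refers to variables thought to affect the outcome, so it is not a pure significance screen.

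Much of this stands as a caution about size. The gain for the slope test is smaller and less certain than for the 6-month comparison. The direction does not change, however. The near-zero slope gains also need strong divergence: with slope SDs of 0.10 and 0.15, the 12-month SD would be √(1 + 144 × 0.01) = 1.6 and √(1 + 144 × 0.0225) = 2.1 times the baseline SD. The first covariate rule is indeed tied to prognosis, but whether it applies is still decided after seeing the data, without a threshold or a list.

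**Conclusion.** The point holds as an improvement to efficiency and pre-specification. It is not an error of validity or sample size. Conditioning on baseline would cut the variance of the 6-month DASH comparison by 15 to 35% if r is 0.7 to 0.3 and the SDs are equal. With a common baseline mean, the variance of the 0 to 12 month slope would fall by about 6 to 23% at a slope SD of 0.05, and by less if slopes vary more. The correlation, the ratio of SDs and the slope SD are all assumptions. The gain shrinks towards zero as r approaches 1 but does not reverse in large samples. The covariate rules should go because they leave the model open without any compensating benefit.

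**What to change.** 1. Replace the t-test with ANCOVA at 6 months on baseline DASH score, blood pressure risk category and medication status. For blood pressure outcomes, use the baseline value of that measure. Alternatively, use the repeated-measures model with baseline means constrained equal across arms.
2. Name one of these as primary. If it is the repeated-measures model, treat time as categorical and report the 6-month contrast, so that it estimates the same quantity as the ANCOVA.
3. In the SAP (Statistical analysis plan) and the protocol (Data Analysis & Statistical Considerations, RCT), delete the testing of baseline differences, the stepwise selection and the discretionary adjustment rule. Describe baseline balance without p-values.

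The cost is protocol and SAP wording only: no new data, visits or participants.

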Missing data: Although we do not expect any missing baseline data, we anticipate no more than 20% missing values in longitudinal outcomes owing to dropout, missed completed dietary recalls, or missed follow-up assessments. In the pilot trial, we had 10% attrition with diet and blood pressure outcomes. Our primary model estimates intervention effects while accounting for missing data.

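### As written, the t-test of 6-month DASH change can include only participants with a 6-month score, because the missing-data method is stated only for the mixed models

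*Combined protocol and SAP*

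**What the plan says.** The Research Abstract defines the endpoint: "The primary outcome is 6-month change in DASH adherence, as measured by 24-hour recalls". The analysis subsection of the SAP first sets a general principle, "All analyses will be based on intention-to-treat (ITT) principles", and then names two analyses of DASH. One is the t-test: "We will assess the overall intervention effect on change of DASH score from baseline to 6 months by a two-sample t-test". The other follows shortly after: "Linear mixed models will be built to test the primary hypotheses". That test is on the interaction of time and arm.

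The closing paragraph of the SAP covers missing data: "Our linear mixed models will be fitted with a full maximum likelihood estimation using all available data to address missing data". It assumes data missing at random (MAR) and names no other analysis. In the protocol (Data Analysis & Statistical Considerations, RCT), the missing-data paragraph likewise refers only to the primary model. It says "we anticipate no more than 20% missing values in longitudinal outcomes" and reports 10% attrition in the pilot. The SAP's sample-size paragraph assumes 20% attrition. No imputation or other rule is given for the t-test. The Aim 1 analysis in the protocol section contains no t-test at all.

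**The concern.** A participant without 6-month recalls has no change score and cannot enter a two-sample t-test unless a value is imputed. At the assumed 20% attrition that is 0.20 × 300 = 60 people. Many of them may have 2- and 4-month DASH scores, which the trial collects in both arms and which this test cannot use.

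The t-test is valid only if, within each arm, those lost resemble those retained in their 6-month change, or if any difference cancels between arms. The arms differ in contact: the intervention arm has coaching zones driven by dietary progress. Dropout that depends on progress in one arm only is therefore conceivable. At stake is the 6-month between-arm difference, which is the trial's stated primary outcome and the quantity a reader will look for.

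**Working it through.** **1. What the sample size rests on.** Inputs from the SAP's sample-size paragraph: difference 1 unit, SD of change 2 in both arms, "With 90% power and a type I error rate (alpha) of .01, a sample size of 242". Sidedness is not stated; two-sided is assumed.

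- Normal approximation: n per arm = 2 × (2.576 + 1.282)² × (2/1)² = 119.1, so 120 per arm and 240 in total.
- Exact t-test solution: 120.7, so 121 per arm and **242** in total, as stated. One-sided gives 210, which does not match.
- Attrition: 242/0.8 = 302.5, or 303; 240/0.8 = 300. The stated 300 is close enough.

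The design is therefore a two-sample comparison of 6-month change. With 20% lost, 120 per arm remain and t-test power is 89.8%. Precision is covered, and the remaining issue is bias.

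**2. Bias formula.** If a fraction d is lost selectively in one arm, bias = d × (mean change of those retained − mean change of those lost). The documents give no value for that gap. For gaps of 0.5, 1 and 2 units:

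- d = 0.20: 0.10, 0.20, 0.40
- d = 0.10: 0.05, 0.10, 0.20

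**3. Simulation with an explicit mechanism.** Assumed inputs: 150 per arm; visits at 0, 2, 4 and 6 months; random-intercept variance 2; slope variance 0.01 per month²; residual variance 1.75. The SD of 6-month change is then √(36 × 0.01 + 2 × 1.75) = √3.86 = 1.96, close to the planned 2. Dropout before month 6 is logistic in one arm, with the odds ratio (OR) given per SD. Entries are absolute bias in DASH units.

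| Dropout depends on | Missing | Estimate | OR 0.5 | OR 0.35 |
|---|---|---|---|---|
| observed 4-month change | 10% | t-test | 0.07 | 0.10 |
| observed 4-month change | 20% | t-test | 0.13 | 0.19 |
| person's true slope | 20% | t-test | 0.08 | 0.11 |
| person's true slope | 20% | likelihood-type | 0.055 | 0.076 |

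The bias favours the intervention if its poorer responders leave, and the control if the control arm's do. When dropout depends on observed change, an estimate using the 0-, 2- and 4-month scores has bias of 0.008 or less. With the same mechanism in both arms the t-test is unbiased. By the formula in step 2, the 20% results imply gaps of 0.13/0.20 = 0.65 and 0.19/0.20 = 0.95 unit.

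A different covariance (SD of change 2 at each visit, correlation 0.5 to 0.7, log-odds 0.5 to 1.0 per SD, about 20% missing) gave t-test estimates of 1.10 to 1.24 for a true 1.0, and 0.99 to 1.01 for the likelihood-type estimate.

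**4. Error rates.** With 120 per arm, SE = √(2 × 3.86/120) = 0.254.

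- Bias 0.13: shift 0.13/0.254 = 0.51; P(Z > 2.07) + P(Z < −3.09) ≈ .020.
- Bias 0.19: shift 0.75; P(Z > 1.83) + P(Z < −3.32) ≈ .034. The simulations give about .02 to .03 overall.
- At 10% missing, 135 per arm, SE = √(2 × 3.86/135) = 0.239: biases of 0.07 and 0.10 give about .013 and .017.
- Power for a true 1 unit at 20% missing: 1/0.254 − 2.576 = 1.36, about 91%. With selective control-arm loss at OR 0.5: 0.87/0.254 − 2.576 = 0.85, about 80% (79 to 80% simulated).

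**The case against.** The strongest reply is that the main inference is already protected. The SAP tests the primary hypotheses with mixed models fitted to all available data under MAR, and the protocol's Aim 1 analysis has no t-test. That stands. A reader might infer that the primary analysis has no missing-data handling; the documents do not support it.

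Three other strong readings also go too far.

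- **That the SAP plans a completers-only analysis.** It never says so. The restriction follows from how the test works when no rule is given.
- **That the intention-to-treat statement is false.** The SAP does not define the principle for missing outcomes. Comparing observed outcomes as randomised may or may not breach it, depending on the definition.
- **That the planned mixed model is unbiased where the t-test is not.** The comparator in the working was a within-arm regression on earlier visits, not the planned linear or quadratic trend model running to 12 months. That model was not simulated.

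One-arm selective dropout is also speculative. Both arms have the same visit schedule and track daily. Entry requires two recalls and four consecutive tracking days. Missing recalls can be completed during the visit, and the 6-month visit is paid. Pilot attrition was 10%, at which the bias is about half.

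Finally, the simulated mechanism suits the remedy. Of the covariance between 4- and 6-month change (0.01 × 4 × 6 + 1.75 = 1.99), 1.75, or 88%, is shared baseline noise. If dropout follows the true slope, the remedy removes only about 30% of the bias (1 − 0.055/0.08).

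These points limit the size and certainty of the concern. They do not give the t-test a missing-data rule.

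**Conclusion.** The point holds in limited form. The t-test, as written, drops everyone without a 6-month score and ignores earlier scores that the trial collects. A better estimate of the same quantity is available at almost no cost. The exposure is limited to the t-test; it matters because no other named analysis gives the 6-month difference directly and the 242 is derived from that difference.

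The size is conditional. For dropout driven by observed 4-month change in one arm (OR 0.5 to 0.35 per SD), the bias is 7 to 10% of the planned effect at 10% missing and 13 to 19% at 20%. These figures rest on the assumed variance components and dropout mechanism, not on anything in the documents. Bias is not certain, and loss that works alike in both arms costs only precision, which the inflation to 300 already covers. The change should be made, but the trial's main test does not depend on it.

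**What to change.** State in the SAP that the 6-month between-arm difference in DASH change is estimated in all randomised participants, by one of two routes:

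- a likelihood model with visit-specific means by arm at baseline, 2, 4 and 6 months, adjusted for the stratification variables already planned, reporting the 6-month contrast with its confidence interval; or
- multiple imputation of the 6-month score within arm from the earlier scores, followed by the comparison.

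If the raw t-test is kept, call it a supportive observed-case analysis, report the number analysed per arm, and say how it relates to the intention-to-treat statement.

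The SAP should also say that either route relies on MAR and does not fully remove bias when dropout depends on the unobserved trajectory. The documents describe no sensitivity analysis for that case; shifting the imputed values in one arm would be a simple one.

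The cost is SAP wording and a few lines of code, with no new data and no change to the sample size.
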